University of Thessaly, School of Health Sciences

Faculty of Medicine

Department of Anesthesiology

STUDY PROTOCOL

A Prospective Observational Study on Assessment of the Soluble Urokinase Plasminogen Activator Receptor in Adult Patients Undergoing Major Non-cardiac Surgery (SPARSE): Study protocol

(SPARSE: if our hypothesis is correct, the SuPAR will help to investigate whether the preoperative suPAR level can aid in identifying patients at high risk for postoperative complications, morbidity and mortality.)

BACKGROUND

Soluble urokinase plasminogen activator receptor

The biomarker soluble urokinase plasminogen activator receptor (suPAR) is the soluble form of the cell membrane-bound protein urokinase plasminogen activator receptor (uPAR), which is expressed mainly on immune cells, endothelial cells, and smooth muscle cells. uPAR is released during inflammation or immune activation, and therefore the suPAR level reflects the extent of immune activation in the individual.¹ All human beings have a baseline level of suPAR that is individually determined and increases with age. Studies have shown that the suPAR level is

associated with morbidity and mortality in a number of acute and chronic diseases and in the general population.²⁻¹⁵ The suPAR level is elevated across diseases, and not solely associated with one specific disease. Therefore, suPAR is applicable as a prognostic marker and not as a diagnostic marker. This characteristic may be utilized for risk stratification in unselected patients.

Originally, uPAR was proven a receptor for urokinase (uPA) which splits plasminogen into active plasmin. Moreover, uPAR interacts with other proteins and plays a role in several important cell processes like migration, adhesion, angiogenesis, proliferation, and chemotaxis.¹ The suPAR protein was discovered in 1991, when it was found to be a marker of cancer progression.¹ In recent years, several studies have shown that suPAR is associated with a number of chronic diseases (including cardiovascular, hepatic, renal, and pulmonary diseases), and that the level is a predictor of a negative outcome of various infectious diseases (tuberculosis, HIV, malaria, sepsis, meningitis, pneumonia) and in critically ill patients.^{2-12, 15,17-21}

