In patients with burn injuries and inhalation trauma requiring mechanical ventilation, the plasma suPAR level and bronchoalveolar lavage fluid level correlate to IL-6 and coagulation factors. An elevated plasma suPAR level is associated with prolonged Intensive Care Unit (ICU) stay and the duration of mechanical ventilation.³¹ The suPAR level is elevated in patients with traumatic brain injury. In trauma patients who suffered a brain injury within 12 hours prior to blood sampling, the mean suPAR level is $14.9 \text{ ng/mL} \pm 6.9$ vs. $2.8 \text{ ng/mL} \pm 0.7$ in control subjects. In

these patients suPAR is associated with severity of the brain injury and with mortality.³²

suPAR in surgery

The suPAR level is elevated in patients with infections, chronic diseases, and cancer compared to healthy individuals. A high suPAR level is associated with increased mortality risk,³³ poor prognosis,³⁴⁻³⁸ postoperative pneumonia,³⁹ and prosthetic joint infection.⁴⁰ suPAR is a well-studied biomarker predicting prognosis, disease severity, and organ dysfunction and is being considered as a marker of the individual's inflammatory status. It has been demonstrated that biomarkers are able to improve triage and are effective in identifying high and low risk patients among acutely admitted patients.⁴¹ Improving the preoperative risk stratification using biomarkers may optimize the patient's clinical outcome.⁴²

Available data on use of biomarkers in addition to risk stratification are observational data, and suPAR has mainly been studied in medical and oncological patients. Gastric surgery patients and orthopedic surgery patients were included in a study conducted in the emergency department at Hillerød Hospital, Denmark. The TRIAGE study included 5992 unselected patients and confirmed the prognostic value of suPAR regarding mortality, and found it similar in both medical and surgical patients.⁴¹ In the same study, it was shown that triage based on suPAR level was superior to the current triage system in predicting 30-day mortality: AUC 0.84 (0.82-0.87) vs. 0.62 (0.58-0.66), respectively. In multivariate analyses of 30-day mortality in relation to suPAR quartiles, adjusted for sex, age, CRP, leucocytes, and triage category, HR was 1.0, 2.2, 8.3, and 26.9 in the upper quartile. A high suPAR level has

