been demonstrated in both tumor tissue and in blood, and in several cancers, the suPAR level is shown to correlate with a poor prognosis.⁴³ In a few studies, suPAR has been studied as a potential biomarker in gastric surgery.

In a cohort of 518 elective colorectal cancer patients, preoperative measurement of the suPAR level was performed. In multivariate analyses adjusted for age, sex, tumor classification, and localization, suPAR was significantly associated with mortality, HR 1.74 (1.33-2.26; $p<0.0001$). In addition, the suPAR level was associated with tumor stage and localization; and in colon cancer patients the suPAR level was significantly higher compared to rectal cancer patients.³⁴ The same cohort was also followed in another study, in which the suPAR plasma level was found to be an independent prognostic marker.³⁵ To identify risk patients among elective colon cancer patients the suPAR level was studied. In patients receiving blood transfusion during surgery, the suPAR level was higher, and a significant association between the suPAR level and postoperative infections was shown. Occurrence of pneumonia was significantly associated with the suPAR level, but any significant association with other infectious complications could not be found.³⁹ In patients with gastric cancer, the suPAR level was significantly higher compared to healthy controls ($2.3 \text{ ng/mL} \pm 0.77$), and the suPAR level was significantly higher in cancer patients with metastatic disease ($7.0 \text{ ng/mL} \pm 6.1$) than in patients with no metastases ($4.8 \text{ ng/mL} \pm 4.4$). In the group of patients with a suPAR value above 5.2 ng/mL , the mortality was significantly increased.³⁶ In patients with rectal cancer and colon cancer, a similar prognostic value is found, indicating an increased mortality risk.^{37,38}

The diagnostic value of suPAR in prosthetic knee/hip joint infection has been examined in a study.⁴⁰ The study included 80 patients of which 45 experienced prosthetic joint infection defined by presence of clinical signs (swelling, redness,

tenderness, and pus inside the joint) and a positive culture. In these patients, a significantly higher median suPAR level (6.8 ng/mL) was found compared to patients without infection, who had revision surgery done. Furthermore, suPAR was positively correlated with CRP, and the study showed that suPAR was more precise in diagnosing prosthetic knee/hip joint infection than CRP.

AIM

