SPARSE is a single-center observational study aiming to investigate if suPAR measured preoperatively and immediately after surgery can predict the risk of future complications and post-operative mortality in adults following major non-cardiac surgery.

METHODS

Design

This is a prospective observational study designed in accordance with the declaration of Helsinki. The study will be register at Clinical Trials.gov and has been approved by the Institutional Review Board of the University Hospital of Larisa, under the reference number 60580/11-12-2018.

Patient eligibility

Consecutive patients who are scheduled to undergo elective major non-cardiac surgery with expected duration ≥ 2 hours under general anesthesia will be screened for

inclusion. All operative approaches will be eligible for inclusion, including open, laparoscopic and robotic procedures. Patients fulfilling the following inclusion criteria will be included: age \geq 18 years, and American Society of Anesthesiologists' (ASA) physical status I to IV.

Exclusion criteria will be age <18 years, any infection within the previous 4 weeks, severe liver disease, patients on renal replacement therapy pre-operatively, patients who had previously received a transplant, patients with allergies, inflammatory or immune system disorders, and/or connective tissue disease including rheumatoid arthritis, ankylosing spondylitis, and systemic lupus erythematosus, administration of steroid, antipsychotic, or anti-inflammatory/immunomodulatory medication during the 3 months prior to surgery, administration of opioids during the past week, asthma, obesity ($BMI \geq 30 \text{ kg m}^{-2}$), mental disability or severe psychiatric disease, alcohol or other abuse, legal incapacity or limited legal capacity, and subjects within the exclusion period of another study.

Management of Anesthesia and Surgical Procedures

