Endotracheal intubation and anesthetic care will be performed according to our institutional routine. Intravenous induction of general anaesthesia will include midazolam 0.15-0.35 mg/kg iv over 20-30 seconds, fentanyl 1 μ g/kg, propofol 1.5-2 mg/kg, ketamine 0.2 mg/kg (intravenous bolus), and rocuronium 0.6 mg/kg. All drugs will be prepared in labelled syringes and induction will be achieved by administration of a predetermined iv bolus dose on the basis of the patient's weight and/or age. Laryngoscopy and intubation will proceed in a standard fashion, while the position of the endotracheal tube will be confirmed by auscultation and

capnography/capnometry. The patients will then connected to an automated ventilator (Draeger Primus®; Drägerwerk AG & Co., Lübeck, Germany).

All patients will be ventilated using a lung-protective strategy with tidal volume of 7 mL/kg, positive end-expiratory pressure of 6-8 cmH₂O, plateau pressures <30 cmH₂O, and recruitment maneuvers repeated every 30 min after tracheal intubation.⁴⁴ Maintenance of general anesthesia will include desflurane 1.0 MAC with 40% oxygen and 60% air, while intraoperative dose changes will be left to the anesthesiologist in charge of the patient. Depth of anesthesia (bispectral index-BIS, Covidien, France) will be monitored, with the target ranging between 40 and 60.^{45,46} Normocapnia will be maintained by adjusting the respiratory rate as needed, while normothermia (37°C) will be maintained throughout the intraoperative period.

All patients will be operated by at least two consultant surgeons who will be supervised by a Professor of Surgery.

Sampling and laboratory measurements

Participants will undergo sampling of peripheral venous blood, immediately after arrival to the OR, and at the Post-Anesthesia Care Unit (PACU). Blood samples drawn from all patients and EDTA plasma will be stored at -80° C until later measurement. Plasma suPAR levels will be determined using the suPARnostic® quick triage lateral flow assay (ViroGates, Denmark), according to the manufacturers instructions.

Microcirculation flow analysis

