Data analysis will be based on predefined data points on a prospective data collection form. The staff will be blinded to measurements until the end of the study and all data are analyzed. Clinical monitoring throughout the study will be performed to maximize protocol adherence, while an independent Data and Safety Monitoring research staff will monitor safety, ethical, and scientific aspects of the study. Data collection will include demographics, anesthesia parameters, C-reactive protein, P-POSSUM score, ACS-NSQIP score, APACHE II, SOFA, and the Charlson Age-Comorbidity Index (Charlson score).⁵⁵ We will use a SAS macro based on ICD-10 diagnoses to calculate the Charlson score.^{56,57} Two other simpler models adding predictive value to the ASA classification will be also used; the Surgical Mortality Probability Model and a similar model proposed by Glance and Donati.^{58,59}

Data management

The goal of the clinical data management plan is to provide high-quality data by adopting standardized procedures to minimize the number of errors and missing data, and consequently, to generate an accurate database for analysis. Remote monitoring is performed to signal early aberrant patterns, issues with consistency, credibility and other anomalies. Any missing and outlier data values are individually revised and completed or corrected whenever possible.

Sample size and predefined statistical analysis plan

Patients will be consecutively included during the study period, in a convenience sample and will be stratified into low-risk or high-risk groups, according to suPAR level (suPAR_{high} above and suPAR_{low} below 5.5 ng/ml), respectively.⁶⁰ An a priori power analysis was done set to detect a difference of 0.50 on the suPAR (between suPAR_{high} and suPAR_{low} group, based on the researchers' preference. The number of patients planned for recruitment was rounded up to 100 to allow for flexibility in the study. This sample size was estimated to achieve 80 percent power to detect the suggested difference. The sample size calculation was made using G*Power 3.1.⁶¹ The association between ASA classification, suPAR level, CRP and the rate of postoperative complications will be analyzed with logistic regression and Cox regression analyses, estimating odds ratios (ORs) and hazard ratios (HRs).

Ethics and dissemination

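### The 80% power statement concerns suPAR itself rather than the outcome, and the form and sample of suPAR used in the regressions are not fixed

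*Combined protocol and SAP*

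**What the plan says.** Under the sample size and predefined statistical analysis plan heading, patients "will be stratified into low-risk or high-risk groups, according to suPAR level (suPAR_{high} above and suPAR_{low} below 5.5 ng/ml". The power analysis was "set to detect a difference of 0.50 on the suPAR (between suPAR_{high} and suPAR_{low} group"; 100 patients are said to give 80% power for that difference. The section gives no significance level, sidedness, standard deviation, unit for the 0.50, or expected share of patients above the cut.

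The analysis sentence reads: "The association between ASA classification, suPAR level, CRP and the rate of postoperative complications will be analyzed with logistic regression and Cox regression analyses". It does not say in what form suPAR enters.

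suPAR is measured twice, "immediately after arrival to the OR, and at the Post-Anesthesia Care Unit (PACU" (Sampling and laboratory measurements). The note under the title asks "whether the preoperative suPAR level can aid in identifying patients at high risk for postoperative complications", whereas the Aim asks if "suPAR measured preoperatively and immediately after surgery can predict the risk of future complications and post-operative mortality". Neither the grouping nor the regression sentence names a sample.

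The primary endpoint (Outcomes) is a composite of complications, ICU admission and mortality in the first 60 postoperative days. No expected event rate is given.

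**The concern.** The study asks whether suPAR predicts what happens to the patient. The only power claim compares suPAR between two groups formed by cutting suPAR, so its outcome variable is also its grouping variable. A reader who takes the 80% as assurance about complications has none.

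Two further gaps concern the main predictor. If the split is what enters the models, a graded relation would be detected less often than with the measured value, and the loss grows as fewer patients exceed the cut. If form and sample remain open, four versions (two forms by two samples) fit the text, and selecting among them by result would raise the false-positive rate.

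**Working it through.** **1. The plan's own figure.** Read 0.50 as a standardised difference d, with equal groups and the normal approximation: n per group = 2(z_α + z_β)²/d².
- One-sided 0.05: 2 × (1.645 + 0.842)²/0.25 = 49.5, so 50 per group and 100 in all (102 by t-test).
- Two-sided 0.05: 2 × (1.960 + 0.842)²/0.25 = 62.8, so 63 per group and 126 in all (128 by t-test); 100 patients give about 70%.

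So 100 fits one set of unstated assumptions. It cannot be derived from the stated inputs alone, and it is not shown to be an arithmetical error.

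**2. What that difference measures.** The background section gives suPAR in gastric cancer as 4.8 ± 4.4 ng/mL (no metastases) and 7.0 ± 6.1 ng/mL (metastatic). Assume a lognormal shape: σ² = ln(1 + (SD/mean)²), μ = ln(mean) − σ²/2.
- 4.8 ± 4.4: σ = 0.781, μ = 1.264. Share above 5.5 = 1 − Φ((1.705 − 1.264)/0.781) = 0.286.
- 7.0 ± 6.1: σ = 0.752, μ = 1.663. Share above 5.5 = 1 − Φ((1.705 − 1.663)/0.752) = 0.478.

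Cut at 5.5, the two groups then differ in mean suPAR by about 7.0 and 7.8 ng/ml (2.3 and 1.7 within-group SDs). With an assumed 3.5 ± 1.5 (mean within the 3-4 ng/mL quoted for emergency patients, SD assumed) the share is 0.096 and the difference 3.6 ng/ml (3.4 SDs). On either scale the difference far exceeds 0.50, and no relation between suPAR and complications was used to get it.

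**3. What 100 patients give for the endpoint.** For one continuous predictor per SD at two-sided 0.05, 80% power needs roughly ln(OR) = 2.802/√(100p(1−p)), where p is the event rate. The simulated column comes from logistic likelihood-ratio tests, 10,000 studies per setting, unadjusted.

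| Event rate (assumed) | OR by formula | OR by simulation |
|---|---|---|
| 10% | exp(2.802/3.000) = 2.5 | 2.8 |
| 20% | exp(2.802/4.000) = 2.0 | 2.1 |
| 30% | exp(2.802/4.583) = 1.8 | 1.9 |
| 40% | exp(2.802/4.899) = 1.8 | 1.8 |

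**4. Split against measured value.** For a normal predictor with share p above the cut point c, the split keeps a fraction φ(c)²/(p(1−p)) of the information: 0.637 at 50%, 0.576 at 30%, 0.342 at 10%. Where the continuous form has 80% power, the split has Φ(2.802√fraction − 1.960) = 61%, 57% and 37%.

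Simulated logistic power (100 patients, 30% events, two-sided 0.05; odds ratios and event rate assumed):

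| Share above 5.5 | Graded, OR 2.0 per SD: continuous | Graded: split | Step at 5.5, OR 4: continuous | Step: split |
|---|---|---|---|---|
| 48% | 0.85 | 0.67 | 0.69 | 0.87 |
| 29% | 0.85 | 0.64 | 0.64 | 0.83 |
| 10% | 0.85 | 0.46 | 0.25 | 0.52 |

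**5. Choosing by result.** With no true effect, 20-30% events and an assumed correlation of 0.5-0.9 between the two samples (20,000 studies per setting):
- one fixed continuous analysis: 5-6%;
- one fixed split analysis: 5-7%, the upper end at shares near 10%;
- better of two forms in one sample: 8-11%;
- best of two forms in two samples: about 12-17% at shares of 29-48%, and up to about 20% at a share near 10%.

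**The case against.** The strongest reply is that the suPAR level plainly means the measured concentration. The background uses it that way, and in the grouping sentence the level is the quantity being cut. On that reading the models are already continuous, the split is descriptive, and the power loss does not arise. This is a fair reading. But the same section builds its groups and its power statement on the split, so the wording does not settle the matter. A reader might infer that the plan commits to a dichotomised analysis and so discards information; the text does not say that.

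The Aim names both samples, so both may simply be reported. That would be a multiplicity question rather than selection. A reader might infer that the analyst will pick the best of four versions; nothing in the documents says so. The 12-20% range describes a risk left open. Its upper end also needs an assumed share near 10%, where the likelihood-ratio test of the split alone rejects about 6-7% of the time.

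A cited, pre-specified cut also suits a study meant to identify high-risk patients, and it wins if risk truly steps there. The background does not establish the shape. Quartile results ("HR was 1.0, 2.2, 8.3, and 26.9 in the upper quartile") point to a gradient, but for 30-day mortality in emergency patients. The report on "the group of patients with a suPAR value above 5.2 ng/mL" is a two-group comparison that cannot separate a step from a gradient. The 29% and 48% shares come from gastric cancer, not from a mixed elective cohort with the exclusions listed under Patient eligibility.

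None of this rescues the 80% statement, which is unrelated to the outcome on any reading.

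**Conclusion.** The power statement is wrong for its purpose: a suPAR difference between groups defined by suPAR follows from the cut, and the 80% tells nothing about the primary endpoint. This rests on no assumption about effect size or event rate. It does not show that 100 patients are too few. That depends on the event rate and the odds ratio, which the documents do not give; on the figures above, 100 patients reach 80% for odds ratios per SD of about 2.8 down to 1.8 as events rise from 10% to 40%, before adjustment for ASA class and CRP.

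The other two consequences are conditional. Power is lost only if the split is the form used and risk is graded, and the size of the loss rests on the assumed odds ratio, event rate and lognormal shape. The false-positive rate rises only if form and sample are chosen by result. The calculations are for unadjusted logistic models; the Cox models were not examined. Nor do the documents show that 5.5 ng/ml is a poor cut. The point should be corrected before analysis.

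**What to change.** 1. Replace the 80% statement with the power, or the confidence-interval width, that 100 patients give for the primary endpoint, with the assumed event rate, effect size, significance level and sidedness stated. The table in step 3 of the working can serve as a starting point.

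2. Name one primary predictor. Suggested text: *The primary predictor in the logistic and Cox models is continuous log2 suPAR from the preoperative sample, reported as an odds or hazard ratio per doubling with 95% CI. The PACU sample analysed in the same way, and the comparison above versus not above 5.5 ng/ml, are secondary analyses.* It would also help to give the expected share above 5.5 ng/ml with its source.

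The cost is a change of wording and a new power calculation; both samples are already planned, so no new data are needed. An effect per doubling is less direct at the bedside, and some power is lost if risk truly steps at the cut. Keeping the cut as a pre-specified secondary analysis limits both drawbacks.

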In addition to routine hemodynamic data, sublingual microvascular flow will be measured using noninvasive technology. We will obtain measurements preoperatively (PRE), intraoperatively (INT), and postoperatively after arrival in the PACU (POST). At each time point, we will image the microcirculatory network of the sublingual mucosa with sidestream darkfield (SDF+) videomicroscopy which has an increased optical resolution resulting in one pixel recording an area of $0.56 \mu\text{m}^2$. This device uses the new SDF+ technology that allows the red blood cells to be visualised with greater accuracy and detail, which is essential for enhancing the capabilities of the analysis application.

We will use the sublingual space as the site of imaging because it shares the same embryologic origin as the splanchnic mucosa and can reflect derangements in splanchnic blood flow; impaired sublingual microcirculatory blood flow is associated with increased mortality and worsening organ failure in patients with sepsis.⁴⁷⁻⁵¹

Outcomes

The primary endpoint will be the presence of complications and/or admission to ICU and/or mortality within the first 60 postoperative days.

Secondary endpoints will be intraoperative complications (including desaturation [$\text{SpO}_2 <92\%$ for 3 minutes or more], need for unplanned recruitment maneuvers, hypotension [defined as systolic blood pressure $<90 \text{ mmHg}$ or mean arterial pressure $<65 \text{ mmHg}$ for 3 minutes or more or need of vasoactive drugs for correction], need for unplanned vasoactive drugs [need for vasoactive drugs not

planned before and/or continuous infusion], and/or acute new arrhythmia [atrial fibrillation, sustained ventricular tachycardia, supraventricular tachycardia, and/or cardiac arrest]), reintubation, hospital length of stay, and length of stay in ICU. Secondary endpoints will also include postoperative complications within 90 days after surgery defined as in the SURPAS studies,⁵²⁻⁵⁴ with the inclusion of atelectasis and ileus, resulting in 22 possible postoperative complications, as well as survival at hospital discharge, at 90 days, and at 1 year.

Data Collection and Monitoring

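### The stated 80% power is for a difference in suPAR between groups defined by suPAR, so it says nothing about the 60-day composite or the planned regressions, and it cannot be checked from the inputs reported

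*Combined protocol and SAP*

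**What the plan says.** All of the sizing is in the section *Sample size and predefined statistical analysis plan*.

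- Patients are a consecutive convenience sample, "stratified into low-risk or high-risk groups, according to suPAR level (suPAR_{high} above and suPAR_{low} below 5.5 ng/ml".
- The effect: "An a priori power analysis was done set to detect a difference of 0.50 on the suPAR (between suPAR_{high} and suPAR_{low} group", chosen "based on the researchers' preference".
- The number was rounded up to 100 from a figure that is not reported, with G*Power 3.1 named as the software. The claim is: "This sample size was estimated to achieve 80 percent power to detect the suggested difference".
- The analysis: "The association between ASA classification, suPAR level, CRP and the rate of postoperative complications will be analyzed with logistic regression and Cox regression analyses".

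The *Aim* section asks whether suPAR "can predict the risk of future complications and post-operative mortality in adults following major non-cardiac surgery". Under *Outcomes*: "The primary endpoint will be the presence of complications and/or admission to ICU and/or mortality within the first 60 postoperative days". No expected event rate, target odds ratio or hazard ratio, event count or interval width for that endpoint appears anywhere.

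**The concern.** The variable that defines the groups is also the variable whose difference is powered. Every patient in the high group has a higher suPAR than every patient in the low group, so a zero difference is impossible and there is no hypothesis to test. The study's real question is whether suPAR relates to clinical events, and this calculation contains no events.

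This is the only power statement in the document, so readers will take it as the power of the study. A null result on the 60-day composite could then be read as adequately powered evidence against suPAR, when the plan gives no basis for that. The calculation also omits the inputs needed to rerun it.

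**Working it through.** **Inputs from the protocol:** difference 0.50, total N = 100, power 80%, cut-off 5.5 ng/ml. **Not given, so assumed:** alpha 0.05, a two-sample t-test, no dropout, and ranges for sidedness, group split and event rate.

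**1. Is the powered contrast informative?** Take suPAR as lognormal with median 2.5 to 5.5 ng/mL and log-SD 0.3 to 0.5 (assumed). Splitting at 5.5 produces group mean differences of 2.7 to 4.8 ng/mL, or 2.1 to 4.6 within-group SDs. These arise from the split alone, with no link to any outcome.

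**2. Can 100 patients and 80% be reproduced with 0.50 as a standardised difference?** The noncentrality is 0.50 × √(n₁n₂/(n₁+n₂)). At 50/50 it is 0.50 × √25 = 2.5, and at 20/80 it is 0.50 × √16 = 2.0. The critical t on 98 df is 1.984 two-sided and 1.661 one-sided.

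| Power at N = 100 | 50/50 | 40/60 | 20/80 | 10/90 | N for 80%, equal groups |
|---|---|---|---|---|---|
| Two-sided | 69.7% | 67.9% | 50.8% | 31.8% | 128 |
| One-sided | 79.9% | 78.5% | 63.4% | 43.8% | 102 |

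Only the one-sided reading with near-equal groups comes close. Even that fits loosely with rounding up to 100, since the t-test needs 102 (the normal approximation gives exactly 100). A fixed cut-off does not assure equal groups. The Background gives 2-3 ng/mL in healthy people and about 3-4 in unselected emergency patients, both below 5.5. Lognormal shapes fitted to its two gastric-cancer groups (4.8 ± 4.4 and 7.0 ± 6.1) put 29% and 48% above 5.5.

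**3. And with 0.50 in ng/mL?** At N = 100, two-sided, 80% power needs a standardised difference of 0.566 at 50/50, so SD = 0.50/0.566 = 0.88. At 20/80 it needs 0.707, so SD = 0.71. The SDs quoted in the Background run from 0.7 to 6.9, which gives power from 94% down to 6.5% at 50/50.

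**4. What do 100 patients give for the composite?** Event rates and effects here are assumptions; tests are two-sided 5%.

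*High/low comparison, 20% events in the low group.* Solve (p₁ − 0.20) = 1.96·√[p̄(1−p̄)(1/n₁+1/n₀)] + 0.842·√[p₁(1−p₁)/n₁ + 0.16/n₀] for p₁:

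| High/low split | Detectable high-group rate | Odds ratio |
|---|---|---|
| 50/50 | 46% | 3.4 |
| 20/80 | 52% | 4.3 |
| 10/90 | 61% | 6.4 |

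Fisher's exact test at these rates has 74-76% power, so the table is slightly optimistic.

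*Continuous suPAR, logistic regression, odds ratio 2.0 per SD, one normally distributed predictor (simulation).* Across repeated runs and Wald and likelihood-ratio tests:

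| Event rate | Unadjusted power | Adjusted power (likelihood ratio) |
|---|---|---|
| 10% | 48-53% | 42-43% |
| 20% | 71-76% | 60-62% |
| 30% | 83-87% | 72-74% |

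The adjusted column adds two covariates, standing in for ASA and CRP, each correlated 0.4 with suPAR. The odds ratio matters as much as the event rate: at 20% events, unadjusted Wald power is about 34% for an odds ratio of 1.5 and 90% for 2.5.

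*AUC precision (Hanley-McNeil), AUC 0.6 to 0.7.* The 95% half-width is about 0.19, 0.14 and 0.12 with 10, 20 and 30 events.

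*Cox regression, high/low, hazard ratio 2.* Events needed = (1.96 + 0.842)²/[p(1−p)(ln 2)²]. At 50/50 this is 7.85/(0.25 × 0.480) = 65.4, so 66. At 20/80 it is 7.85/(0.16 × 0.480) = 102.2, so 103. With 30 events, power is 48% and 33%.

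**The case against.** Four points deserve weight.

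- *No arithmetic error is proved.* This stands. A one-sided 5% test with equal groups lands at 79.9%. The fault is that the powered quantity is not the study's endpoint and that the inputs are missing.
- *The sentence may be garbled.* Its bracket is never closed, and the authors may have meant a standardised effect on some outcome compared between suPAR groups. That cannot be shown from the text, which places the difference on suPAR. Even on that reading, a standardised mean difference is not the effect measure for a binary composite analysed by logistic or Cox regression, and the inputs would still be missing.
- *It is a convenience sample, so power is secondary.* The study may proceed on that basis. But having claimed 80% power in advance, the plan must claim it for its own question.
- *The replacement figures are assumption-driven, and log suPAR and the AUC are not in the plan.* This is fair. The figures should be shown as a range over both event rate and effect size, and as a description rather than a commitment to new analyses. The defect itself needs no assumed rate.

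**Conclusion.** The concern holds. The 80% belongs to a contrast that the cut-off makes non-zero, and no passage gives power or precision for the 60-day composite or the regressions. This conclusion rests on the protocol's wording alone.

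The sizes depend on assumptions. The plan's own figure ranges from 79.9% (one-sided, equal groups) to 50.8% (two-sided, 20/80) with 0.50 as a standardised difference, and more widely still if it is in ng/mL. For the composite, 100 patients support a high/low comparison only for large effects. Continuous suPAR does better, but its power runs from about one half to about 85% for an odds ratio of 2.0 per SD as the event rate goes from 10% to 30%, and is lower after adjustment. The sample size of 100 is not itself shown to be wrong.

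**What to change.** Withdraw the claim of 80% power for a 0.50 difference in suPAR. Keep 100 as the convenience sample, say that it was not sized on the primary endpoint, and state what it delivers. For example:

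> The sample of 100 was not sized on the primary endpoint. If 10%, 20% or 30% of patients have the 60-day composite, power (two-sided 5%) for an odds ratio of 2.0 per SD of log suPAR as a single normally distributed predictor is about 50%, 74% and 85%, and lower after adjustment for ASA and CRP. At 20% events, power is about 34% for an odds ratio of 1.5 and 90% for 2.5. The 95% half-width of the AUC is about 0.19, 0.14 and 0.12 at the three event rates. For the high/low comparison with 20% events in the low group, the high-group rate detectable with about 80% power (normal approximation; 74-76% by Fisher's exact test) is 46%, 52% and 61% at 50/50, 20/80 and 10/90 splits.

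If suPAR will not be log-transformed or no AUC is intended, adapt or drop those phrases. Add the Cox event counts if the Cox model is to carry a main conclusion. If the G*Power calculation is kept as a record, report its test, alpha, sidedness, unit of 0.50, SD, allocation ratio and the number before rounding.

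The cost is one reworded paragraph and a less favourable stated figure. Patient number, endpoint and planned regressions are unchanged.
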